# 8.3.7 Knee/Wrist MRI/X-ray

Yearly growth assessments require integration of information including height measurements and bone age if clinically indicated, which should be plotted onto growth charts. Children with impaired growth velocity should be referred to a paediatric endocrinologist as clinically indicated for evaluation, and should be followed until they reach final adult height.

An MRI/X-ray of the knee will be performed at screening as specified in Table 2 and Table 3, and if clinically indicated, to monitor growth plates for any signs of physeal dysplasia. The imaging modality that is used at baseline (MRI/X-ray) must be used at all follow-up visits throughout the study. A wrist MRI/X-ray is acceptable if it is not possible to perform knee MRI/X-ray. The joint imaged (left/right, wrist/knee) must be consistent throughout the study, except occasions where MRI/X-ray of the joint imaged at baseline is not possible. Where feasible the knee/wrist MRI/X-ray will be performed at the same time as the PN volumetric MRI.

The investigator should regularly look for signs of physeal dysplasia (eg, joint pain and fatigue after exercising, abnormal gait, and spine irregularities). Children who show signs of physeal dysplasia at the time of selumetinib discontinuation should have a follow-up assessment after 30 days to evaluate the potential for reversibility.

## 8.3.8 **Performance Status**

Performance status will be measured as indicated in the SoA; the Lansky performance scale is described in more detail in Appendix G.

Any significant change from baseline or screening must be reported as an AE.

## 8.3.9 Clinical Safety Laboratory Assessments

Blood and urine samples for determination of clinical chemistry, haematology and urinalysis will be taken at the visits indicated in the SoA.

Additional safety samples may be collected if clinically indicated at the discretion of the Investigator. The date, time of collection, and results (values, units and reference ranges) will be recorded on the appropriate eCRF.

The clinical chemistry, haematology and urinalysis will be performed at a local laboratory at or near to the investigator site. Sample tubes and sample sizes may vary depending on laboratory method used and routine practice at the site.

The laboratory variables shown in Table 13 will be measured.
#### Clinical Study Protocol -5.0 Selumetinib - D1346C00004 **Table 13** Laboratory Safety Variables

Haematology/Haemostasis (whole blood)	Clinical chemistry (serum or plasma)
B – Haemoglobin	S/P – Albumin
B – Platelet count	S/P – Alkaline phosphatase
B – Leukocyte count	S/P – Alanine aminotransferase
B – Leukocyte differential count (absolute count)	S/P – Aspartate aminotransferase
B – Absolute Neutrophil count	S/P – Total calcium
B – Absolute Lymphocyte count	S/P – Creatinine a
B – Total white blood cell count	S/P – Gamma-glutamyl transferase
B – Total red blood cell count	S/P – Magnesium
	S/P – Phosphate
	S/P – Potassium
	S/P – Sodium
Urinalysis (dipstick) b	S/P – Total protein
U – Glucose	S/P – Total bilirubin
U – Protein/albumin	S/P – Urea nitrogen c
U – Haemoglobin/erythrocytes/blood	S/P – Creatine kinase d
	S/P – Amylase
	S/P – Troponin (isoform per site norm) e

a. Creatinine clearance and glomerular filtration rate to be calculated at screening and if clinically indicated.

b. Urine microscopy will be assessed if other urinalysis measurements are abnormal or if clinically indicated

c. Urea or blood urea nitrogen based on local site practice.

d. Creatine Kinase to be assessed in accordance with the schedule of assessments and if unexplained muscle weakness or myalgia (muscle pain) occurs. See Section 8.3.1 for additional information.

e. Troponin (isoform per site norm), should be assessed at screening, and performed when there is a significant drop in LVEF (of ≥10 percentage points relative to baseline and to an absolute LVEF below the institution's LLN on study intervention) or for any cardiorespiratory events with no obvious diagnosis. If troponin assessments are not available, per local practice, CK-MB isoform should be assessed. Participants should be managed according to the algorithm provided in Appendix E 2.

B, blood; CK-MB, creatine kinase-myocardial band; LLN, lower limit of detection; LVEF, left ventricular ejection fraction; P, plasma; S, serum; U, urine.

In case a participant shows an AST or  $ALT \ge 3 \times ULN$  together with total bilirubin  $\ge 2 \times ULN$  please refer to Appendix D, Actions required in cases of increases in liver biochemistry and evaluation of Hy's Law, for further instructions.

The Investigator should assess the available results with regard to clinically relevant abnormalities. Any clinically significant abnormal laboratory values should be repeated as clinically indicated and recorded on the eCRF. Situations in which laboratory safety results should be reported as AEs are described in Section 8.4.5.

Clinical Study Protocol -5.0 Selumetinib - D1346C00004 All participants with Grade 3 or 4 laboratory values at the time of completion or discontinuation from study intervention must be followed and have further tests performed until the laboratory values have returned to Grade 1 or 2, unless these values are not likely to improve because of the underlying disease.

#### 8.3.10 **Other Safety Assessments**

8.3.10.1

will be used based on age of the participant at the time of the Appropriate **CC** assessment:

The C	Cl consists of CCl		
CCI			
CCI		The CCI	consist of
CCI	In the context of t	his study CCI	
CCI	BothCCI	includeCC	. The CCI
CCI	are used to compute the CC	score and CCI	scores: CCI
		The CCI	measure aspects of
CCI			The CCI
CCI	takes approximately	CI minutes to comple	te CCI The
CCI	of participants aged CCI y	ears will be evaluated with this	test.

Clinical Study Protocol -5.0		AstraZeneca
Selumetinib - D1346C00004		
CCI		
The CCI	, currently in its CCI edition, is a w	videly used and
accepted test of CCI	. In the context of this study, only the CCI	is required,
there is no need to perform CCI		
The CCI is validated for administra	tion to people aged CCI years (there is no uppe	er limit) and
takes CCI minutes to complete. The	of participants aged CCI yea	ars will be
evaluated with this test CCI		

# 8.4 Adverse Events and Serious Adverse Events

The Principal Investigator is responsible for ensuring that all staff involved in the study are familiar with the content of this section.

The definitions of an AE or SAE can be found in Appendix B.

Adverse events will be reported by the participant (or, when appropriate, by a caregiver, surrogate, or the participant's legally authorised representative).

The Investigator and any designees are responsible for detecting, documenting, and recording events that meet the definition of an AE.

# 8.4.1 Time Period and Frequency for Collecting AE and SAE Information

Adverse events will be collected from the time of signature of the ICF until 30 days after the last dose of selumetinib or 25 cycles of treatment, whichever is earlier. For participants taking part in the long term safety follow-up (participants < 5 years of age), after 25 cycles of treatment or end of treatment, adverse events causally related to selumetinib will be collected until they complete the study in accordance with Table 3. No AEs will be collected for participants who are > 5 years of age who remain in the study after 25 cycles of treatment.

SAEs will be collected from time of signing the ICF throughout a subject's participation in the study.

If the Investigator becomes aware of an SAE with a suspected causal relationship to the IMP that occurs after the end of the clinical study in a participant treated by him or her, the Investigator shall, without undue delay, report the SAE to the Sponsor.

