### **Intervention Group and Duration:**

This study consists of a screening period (up to 28 days), a treatment period (25 cycles) and a long term safety follow-up for participants until they are 5 years old or commence an

alternative systemic NF1-PN treatment, whichever is the earlier. Participants may continue treatment with selumetinib throughout the long term safety follow-up as long as they are considered to be receiving clinical benefit in the opinion of their Investigator. A safety follow-up assessment will be performed 30 days after the last dose of study intervention for all study participants.

Selumetinib will be administered using BSA-based dosing. The granule formulation dose schema to be used in the study will be established in the dose-finding phase.

At enrolment participants must have a BSA within the range 0.40 to 1.09 m^2; once participants attain a BSA between 1.10 and 1.29 m^2 they will be encouraged to transition to the capsule formulation, if feasible, although all participants must remain on the granule formulation until after they have completed their third cycle of treatment.

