## **1.3** Schedule of Activities

Procedure	Screen		Intervention Period in Cycles (28-day cycle) a														EoT Safety Follow-up (30 days after last dose)	Section or Appendix	
		C1 D1	C1 D15	C2 D1	C3 D1	C4 D1	C5 D1	C7 D1	C9 D1	C11 D1	C13 D1	C17 D1	C19 D1	C21 D1	C25 D1	Day 7 after transition to capsule formulation b	EoT °		
Weeks		1	3	5	9	13	17	25	33	41	49	65	73	81	97				
Window (days)	-28 to - 1	0	± 3	± 3	± 3	± 3	± 3	± 3	± 3	± 3	± 3	± 3	± 7	± 3	± 3	+ 4 to 14	+7	+ 7	
Informed consent z	X																		A 3
Inclusion and exclusior criteria	X																		5.1, 5.2
Demography	Х																		5.1, 5.2
Full Physical examination including standard neurological examination	x			x	x	x	x	x	x	x	x	x		x	x		х	Х	8.3.1
Abbreviated physical examination		х	X																8.3.1
Height, weight	Х	Х	Х	Х	Х	Х	Х	Х	Х	Х	Х	Х		Х	Х	Х	Х	Х	8.3.2
BSA d	X	Х		Х	Х	Х	Х	Х	Х	Х	Х	Х		Х	Х	Х			8.3.2
Disease characteristics e	X																		
Medical history	X										1								5.1, 5.2

Procedure	Screen		Intervention Period in Cycles (28-day cycle) a														EoT Safety Follow-up (30 days after last dose)	Section or Appendix	
		C1 D1	C1C2C3C4C5C7C9C11C13C17C19C21C25Day 7 after transition to capsule formulation bD15D1D1D1D1D1D1D1D1C13C17C19C19C21C25Day 7 after transition to capsule formulation bEoT c																
Weeks	ľ	1	3	5	9	13	17	25	33	41	49	65	73	81	97				
Window (days)	-28 to - 1	0	± 3	± 3	± 3	± 3	± 3	± 3	± 3	± 3	± 3	± 3	± 7	± 3	± 3	+ 4 to 14	+ 7	+ 7	
Clinical safety lab assessments f	X	Х	Х	Х	Х	Х	Х	Х	Х	Х	Х	Х		Х	Х		Х	Х	8.3.9
12-lead ECG	Х			Х			Х		Х		Х	Х		Х	Х		Х	Х	8.3.4
Echocardiogram g	X			Х			Х		Х		Х	Х		Х	Х		X g	X g	8.3.5
Ophthalmology examination h	X			Х			Х		Х		Х			Х			Х	X h	8.3.6
Knee MRI/X-ray (Physeal dysplasia) i	X										Х				Х				8.3.7
Performance status f	X	Х	Х	Х	Х	Х	Х	Х	Х	Х	Х	Х		Х	Х		Х	Х	8.3.8
Urinalysis f	Х	Х	Х	Х	Х	Х	Х	Х	Х	Х	Х	Х		Х	Х		Х	Х	8.3.9
Vital signs	Х	Х	Х	Х	Х	Х	Х	Х	Х	X	Х	Х		Х	Х		Х	Х	8.3.3
PN assessments using volumetric MRI j	X						Х		Х		Х		Х		Х		As	per SoC j	8.2.1

	Procedure	Screen		Intervention Period in Cycles (28-day cycle) a											EoT Safety Follow-up (30 days after last dose)	Section or Appendix				

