			C1 D1	C1 D15	C2 D1	C3 D1	C4 D1	C5 D1	C7 D1	C9 D1	C11 D1	C13 D1	C17 D1	C19 D1	C21 D1	C25 D1	Day 7 after transition to capsule formulation b	EoT °		
Weel	ks		1	3	5	9	13	17	25	33	41	49	65	73	81	97				
Wind	dow (days)	-28 to - 1	0	± 3	± 3	± 3	± 3	± 3	± 3	± 3	± 3	± 3	± 3	± 7	± 3	± 3	+ 4 to 14	+ 7	+ 7	

Procedure	Screen		Intervention Period in Cycles (28-day cycle) a														EoT Safety Follow-up (30 days after last dose)	Section or Appendix	
		C1 D1	C1 D15	C2 D1	C3 D1	C4 D1	C5 D1	C7 D1	C9 D1	C11 D1	C13 D1	C17 D1	C19 D1	C21 D1	C25 D1	Day 7 after transition to capsule formulation b	EoT °		
Weeks		1	3         5         9         13         17         25         33         41         49         65         73         81         97																
Window (days)	-28 to - 1	0	$\begin{array}{ c c c c c c c c c c c c c c c c c c c$											+ 7	+ 7				
Palatability (Observer Palatability) s		daily C1W 1						Twice daily C7W1											8.2.7.6
Dispense medication t		Х		Х	Х	Х	Х	Х	Х	Х	Х	Х	Х	Х	Х				6
Return medication/compliance check				Х	Х	Х	х	Х	Х	Х	Х	Х	Х	Х	Х		Х		6.2 6.4
Dispense/return ePRO device/review ePROs	Х	Х	Х	Х	Х	Х	Х	Х	Х	Х	Х	Х		Х	Х	Х	Х		6.4
Daily Drug Diary		←===						t	wice da	aily ==						→			6.4
Review Daily Drug Diary			Х	Х	Х	Х	Х	Х	Х	Х	Х	Х		Х	Х	X	Х		6.4
Blood for PD Biomarkers u		Х																	8.6.2

Procedure	Screen		Intervention Period in Cycles (28-day cycle) a Follow (30 da after 1 dose													EoT Safety Follow-up (30 days after last dose)	Section or Appendix		
		C1 D1	C1C2C3C4C5C7C9C11C13C17C19C21Day 7 after transition to capsule formulation $b$ D15D1D1D1D1D1D1D1D1D1D1D1																
Weeks		1	3	5	9	13	17	25	33	41	49	65	73	81	97				
Window (days)	-28 to - 1	0	± 3	± 3	± 3	± 3	± 3	± 3	± 3	± 3	± 3	± 3	± 7	± 3	± 3	+ 4 to 14	+ 7	+ 7	
PK blood samples v, w		Х		Х			Х				Х				х	X			8.6.1.1
Adverse Events x	X	←==															>	Х	8.4
Concomitant medication/ procedures	X	←==															===→	Х	6.5
NF1 treatments y			←===				collect	for par	rticipan	ts who	discon	tinue se	elumeti	nib prio	or to C	25 =====		=====→	

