- x. Adverse events will be collected from the time of signing the informed consent form, throughout the treatment period, and including the follow-up period.
- y. Other systemic NF1-PN targeted treatments will be collected for all participants who discontinue selumetinib until the time when they would have completed 25 cycles of treatment, or they commence an alternative systemic NF1-PN treatment whichever is the earliest.
- z. Consent can be performed on Day -42 onwards. All screening assessments must be performed within 28 days prior to dosing.

CCI	; BSA, body surface area; C, cycle; CSP, Clinical Study Protocol;
D, day; CCI	; ECG, electrocardiogram; EDC, electronic data capture; EoT, end of treatment; CC
CCI	; FU, follow-up; CCI
CCI	LLN, lower limit of normal; LVEF, left ventricular ejection fraction; MRI, magnetic resonance imaging; NF1, neurofibromatosis
type 1; PD, pharmacodynamic	: CC : PK, pharmacokinetic(s): PN, plexiform neurofibroma: SoC, standard of care;

VMI, Visual-Motor Integration; W, week.

AstraZeneca

	Participants receiving selumetinib treatment a			Participants no longer receiving selumetinib treatment		
Procedure b	Every 6 cycles	Every 12 cycles	EoT Safety Follow-up (30 days after last dose)	Every 6 months	Every year	Section or Appendix
Window	±7 days	±7 days	+ 7 days	± 7 days	±7 days	
Full Physical examination	Х		X	Х		8.3.1
Height, weight	Х		X	Х		8.3.2
BSA	Х			Х		8.3.2
Clinical safety laboratory assessments	Х		X	Х		8.3.9
12-lead ECG	Х		Х	If clinically	y indicated	8.3.4
Echocardiogram	Approximately	every 3 cycles	Х	If clinically indicated		8.3.5
Ophthalmology examination		X	Х	If clinically	y indicated	8.3.6
Knee MRI/X-ray (Physeal dysplasia)		X			Х	8.3.7
Performance status	Х		Х	Х		8.3.8
Urinalysis	Х		Х	Х		8.3.9
Vital signs	Х		Х	Х		8.3.3
CI	1	1				
Dispense medication d	To be dispensed	l every 2 cycles				6
Return Medication/Compliance Check		>	Х			6.2 6.4
SAEs and AEs causally related to selumetinib	←======	→	Х	← =======	→	8.4

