## 4.1.2 Overall Design

This is a Phase I/II, single-arm, open-label study in children aged  $\ge 1$  to < 7 years at study entry (date of ICF signature) with a clinical diagnosis of NF1-related symptomatic, inoperable PN. The

Participants will receive selumetinib for 25 cycles (or until they meet discontinuation criteria).

Enrolment into the Global Cohorts (Cohorts 1 and 2) will be stratified by age group:

- Cohort 1: participants enrolled outside Japan aged between  $\geq$  4 and < 7 years
- Cohort 2: participants enrolled outside Japan aged between  $\geq 1$  to < 4 years

After completion of at least one cycle (28 days) of dosing in 3 evaluable participants in Cohort 1, SRC will review the emerging safety and PK data. Providing the single dose PK exposure is within the acceptable range and there are no safety concerns as determined by SRC then dosing in Cohort 2 will be initiated and additional participants will be dosed in Cohort 1. If the PK exposure is not within the acceptable range, the dose may be adjusted to ensure that selumetinib exposure is within the range observed in the SPRINT study; PK will be assessed against acceptance criteria in an additional 3 evaluable cohort 1 participants who received the adjusted dose. Cohort 2 will be initiated once the selumetinib granule formulation dose schema is identified for Cohort 1. The physiologically-based PK model will be updated, if required, based on emerging PK data.

Additional SRC reviews will be held for each of the cohorts following at least one cycle of dosing in approximately 6 evaluable participants and again in approximately 10 evaluable participants. The SRC will evaluate the PK, safety and tolerability of the granule formulation for that dose schema. The Japan cohort will not participate in dose-finding phase. Further information on the SRC can be found in Section 9.6.In addition to the Global Cohorts, Japanese participants in Japan aged between  $\geq 1$  to < 7 years with NF1 related symptomatic, inoperable PN will be enrolled into the Japan Cohort.

At enrolment participants must have a BSA within the range 0.40 to 1.09 m^2; once participants attain a BSA between 1.10 and 1.29 m^2 they will be encouraged to transition to the capsule formulation, if feasible, although all participants must remain on the granule formulation until after they have completed their third cycle of treatment.

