4.6.2 Adverse Events

4.6.2.1 Definitions and Derivations

The MedDRA version 26.1 or higher is used to code AEs. AEs are graded according to the CTCAE version 5.0.

AEs will be collected from the time of signature of the ICF until 30 days after the last dose of selumetinib or 25 cycles of treatment, whichever is earlier. For participants taking part in the long-term safety follow-up (participants < 5 years of age), after 25 cycles of treatment or end of treatment, AEs causally related to selumetinib will be collected until they complete the study in accordance with CSP Table 3. The long-term safety follow-up is designed to assess the long-term safety of selumetinib treatment in participants who are < 3 years of age when they commence selumetinib, as there are no long-term safety data currently available for patients who received selumetinib at this age. No AEs will be collected for participants who are > 5 years of age who remain in the study after 25 cycles of treatment.

A treatment-emergent AE will be defined as an AE that starts, or worsens, after the first dose of selumetinib up to and including 30 days after the last dose of selumetinib.

AEs of special interest

Some clinical concepts (including some selected individual preferred terms and higher-level terms) have been considered AESIs to the selumetinib program.

The AESIs in [Table 16](#) have been identified as a list of categories by the patient safety team.

Table 16 **AEs of special interest**

AESI	MedDRA Preferred Terms Defining the AESIs
Ocular toxicity	Chorioretinopathy (central serous retinopathy [CSR]); Retinal detachment; Retinal tear; Vision blurred; Visual impairment; Vitreous floaters; Photopsia; Eye disorder; Photophobia; Retinal vein occlusion (RVO); Detachment of retinal pigment epithelium (Retinal pigment epithelial detachment [RPED]).
Hepatotoxicity	Drug-induced liver injury; ALT increased; AST increased.
Muscular toxicity	Blood creatine phosphokinase increased; Musculoskeletal pain; Muscular weakness; Myalgia; Rhabdomyolysis; Myoglobin blood increased; Myoglobin urine present; Acute kidney injury; Myopathy.
Cardiac toxicity	Ejection fraction decreased; Oedema peripheral; Peripheral swelling; Oedema; Left ventricular dysfunction; Ventricular dysfunction.
Physeal dysplasia	Metaphyseal dysplasia; Multiple epiphyseal dysplasia; Arthralgia; Joint stiffness; Joint hyperextension; Gait disturbance; Short stature.
Choking on the capsule	Choking; Retching.

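### Protocol 8.4.1 and SAP 4.6.2.1 can be read as ending general AE collection at 25 cycles, which conflicts with the scheduled 30-day AE assessment and the SAP's treatment-emergent window for children who stop at about Cycle 25

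*Protocol*

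**What the plan says.** Protocol 8.4.1 collects AEs from consent "until 30 days after the last dose of selumetinib or 25 cycles of treatment, whichever is earlier". SAP 4.6.2.1 uses the same wording. The next two sentences of 8.4.1 give the rules that then take over. For children under 5 in long-term follow-up, only causally related AEs are collected after 25 cycles or end of treatment. For children over 5 who remain in the study after 25 cycles, no AEs are collected. Serious AEs (SAEs) are collected throughout participation.

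Other places give a different end point:

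- Protocol 1.3, Table 2, marks the AE row at the safety follow-up visit 30 days after last dose. Its footnote x reads "Adverse events will be collected from the time of signing the informed consent form, throughout the treatment period, and including the follow-up period".
- The synopsis, under Intervention Group and Duration, states: "A safety follow-up assessment will be performed 30 days after the last dose of study intervention for all study participants".
- SAP 4.6.2.1 defines a treatment-emergent AE as one that starts or worsens after the first dose "up to and including 30 days after the last dose of selumetinib".

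On children under 5 who discontinue, footnote a of Table 2 sends them to Table 3, which collects only SAEs and causally related AEs.

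**The concern.** Treatment is planned for 25 cycles, so stopping at the end of Cycle 25 is an ordinary path through the study. For a child on that path, the earlier of the two limits in 8.4.1 is the end of Cycle 25. Read literally, routine AE collection closes on the last dosing day, although the schedule has an AE assessment 30 days later and the SAP counts events up to that day as treatment-emergent. The reporting window is then longer than the collection window.

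Safety and tolerability form a primary objective. The protocol treats the 30-day visit as informative: it schedules laboratory tests, vital signs, ECG and physical examination, and repeats the echocardiogram or eye examination where there was an earlier abnormality. A clinically relevant deterioration found there is normally reportable as an AE (8.4.5), and events of special interest may be non-serious (8.4.13). A child who stops well before Cycle 25 keeps the full 30 days under the first sentence of 8.4.1, while one who stops at Cycle 25 may not.

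**Working it through.** The plan gives no figure of its own here. The check is day arithmetic, followed by a comparison of the passages.

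**Inputs**

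- Cycle length: 28 days (Table 2).
- Planned treatment: 25 cycles (Protocol 4.1.2). End of Cycle 25 = 25 × 28 = Day 700. Cycle 25 Day 1 = 24 × 28 + 1 = Day 673, which falls in week 97 as in Table 2.
- L = study day of the last dose, for a child who stops by Day 700.

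**Formulas**

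- Hard-stop reading of 8.4.1: collection ends at min(L + 30, 700).
- Schedule and SAP treatment-emergent window: ends at L + 30.
- Alternative reading, 30 days after the earlier of last dose and 25 cycles: ends at min(L, 700) + 30.
- Days lost = (L + 30) minus the collection end. On the hard-stop reading this is max(0, L − 670).

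| Last dose (L) | Hard-stop end | Schedule/SAP end | Lost, hard stop | Lost, alternative |
|---|---|---|---|---|
| Day 670 | 700 | 700 | 0 | 0 |
| Day 671 | 700 | 701 | 1 | 0 |
| Day 673 (Cycle 25 Day 1) | 700 | 703 | 3 | 0 |
| Day 686 | 700 | 716 | 16 | 0 |
| Day 700 (end of Cycle 25) | 700 | 730 | 30 | 0 |

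At the extreme, 30 of 730 days of the treatment-emergent window (4.1%) go uncollected, and these are all of the off-drug days.

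**Which reading the text favours.** The two sentences that follow in 8.4.1 switch to a reduced rule, or to none, once 25 cycles are complete, with no 30-day overlap. That fits the hard stop. The alternative reading fits Table 2, footnote x, the synopsis and the SAP window better. Both are plausible.

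**Which events are at risk on the hard-stop reading**

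- SAEs: none lost, at any age.
- Child under 5 who enters long-term follow-up: causally related AEs are kept, so only non-serious AEs judged unrelated are lost.
- Child aged 5 or over: no long-term follow-up applies, so all non-serious AEs in the lost days are at risk. A child reaches 5 by Day 700 if first dosed at 5 − 700/365.25 = 3.08 years or older. That covers all of Cohort 1 (aged 4 or over at entry) and the older part of Cohort 2.

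**Separate ambiguity, not dependent on the reading above.** For a child under 5 who stops early, the first sentence of 8.4.1 asks for all AEs for 30 days after last dose. The second asks for only causally related AEs after end of treatment. Table 2 (all AEs at the 30-day visit) and Table 3 (SAEs and related AEs only) mirror the same split.

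**The case against.** The strongest answer is that the schedule already collects these events. AEs are marked at the 30-day visit, Protocol 8.3 refers to the schedule for the timing of safety assessments, and Section 8 makes adherence to it mandatory. A site following Table 2 would record everything, and the alternative reading of 8.4.1 gives the same result with no loss. This stands. It makes the fault an inconsistency that sites may resolve differently, not a demonstrated omission.

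The examinations and laboratory tests at the 30-day visit also remain, so abnormal findings would be in the data even where no AE was recorded. This stands too, and it limits the consequence.

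On early stoppers under 5, Tables 2 and 3 can be read in sequence: the Table 2 30-day visit first, then Table 3. That is a sensible reading, but 8.4.1 does not say so.

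A reader might infer more than the documents support:

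- That children who complete 25 cycles contribute no non-serious events to the treatment-emergent window. They do contribute: the window opens at first dose, so up to about 700 days are collected and only the tail is in question.
- That the children affected are those with the longest exposure. Children who continue beyond Cycle 25 have longer exposure and are outside this point.
- That drug-related late events are lost throughout. In children under 5 in long-term follow-up, causally related events are kept.
- That a study-wide total of lost follow-up can be given. The planned number of participants is redacted and the number who will stop at Cycle 25 is not stated.

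**Conclusion.** The concern holds as an internal inconsistency with a bounded consequence. On the reading that its own next sentences favour, Protocol 8.4.1 (and SAP 4.6.2.1) contradicts Table 2, footnote x, the synopsis and the SAP's treatment-emergent definition. For a child who stops at about Cycle 25 with a last dose after Day 670, up to 30 days of post-dose collection of non-serious AEs can be lost, with the age split shown above. Children who stop on or before Day 670 lose nothing through this clause.

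This rests on 28-day cycles without delay and on the hard-stop reading. On the alternative reading the loss is zero. The documents therefore support a risk of inconsistent collection between sites. They do not show systematic loss or a bias of known size. The ambiguity for children under 5 who stop early is a second, separate item that the same edit should settle.

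**What to change.** Reconcile Protocol 8.4.1 and SAP 4.6.2.1 with Table 2, footnote x and Table 3, using identical wording in both documents:

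- For every child who permanently stops selumetinib at or before completing the Cycle 25 treatment period, all AEs are collected until 30 days after last dose. The Cycle 25 treatment period should expressly include the scheduled visit windows (±3 days at Cycle 25 Day 1, +7 days at end of treatment), so that a last dose a few days after Day 700 is not treated as continuation.
- This includes children under 5. The related-only rule of Table 3 begins after those 30 days.
- For children who continue on selumetinib after Cycle 25, the existing Table 3 or SAE-only rules apply from the end of Cycle 25.

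The cost is a short rewording in each document and matching notes to the two schedules. The 30-day visit and its AE assessment are already planned, so no visit or procedure is added. The SAP's treatment-emergent definition needs no change for children who stop by the end of Cycle 25.
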